9.2.1.2 Assessment of Adverse Events

For each AE, the start and resolution dates, intensity, seriousness (i.e., whether the event meets the definition of an SAE (Section 9.3.1), relationship of the event to the study drug, action taken regarding study drug, and outcome of the event will be documented on the eCRF.

Intensity

The following definitions should be used to assess and grade AE intensity, including laboratory abnormalities judged to be clinically significant.

Page 38 of 74

Severity Grade		Description
Mild	1	Awareness of sign or symptom, but easily tolerated
Moderate 2		Discomfort enough to cause interference with usual activity
Severe	3	Incapacitating with inability to work or do usual activity

Note: a severe adverse event is not necessarily serious.

Relationship

The relationship of an AE to study drug should be assessed using the guidelines presented in the table below. An AE for which there has been no causal relationship reported will require follow-up to determine causality.

Degree of Certainty	Description
Definitely Related	An event that follows a reasonable temporal sequence from administration of the test article; that follows a known or expected response pattern to the test article; and that is confirmed by improvement on stopping or reducing the dosage, and reappearance of the event on repeated exposure (re-challenge).
Probably Related	An event that follows a reasonable temporal sequence from administration of the test article; that follows a known or expected response pattern to the test article; and that is confirmed by improvement on stopping or reducing the dosage of the test article; and that is unlikely to have been caused by concurrent/underlying illness or other drugs, procedures, or other causes.
Possibly Related	An event that follows a reasonable temporal sequence from administration of the test article; that follows a known or expected response pattern to the test article; but may have been caused by concurrent/underlying illness, other drug, procedure, or other causes.
Unlikely Related	An event that does not follow a reasonable temporal sequence from administration of the test article; that does not follow a known or expected response pattern to the test article, or most likely was caused by concurrent/underlying illness, other drug, procedure, or other causes, because of their known effects.
Not related	An event almost certainly caused by concurrent/underlying illness, other drug, procedure, or other causes.

Adverse Event Relationships to Study Drug

Outcome

Each AE will be characterized according to the outcomes described in the following table:

SprickellBiotech

Page 39 of 74

Outcome	Description
Recovered/Resolved	The subject has fully recovered from the event with no observable residual effects.
Recovering/Resolving	The effects of the event are improving, or events have stabilized (are constant and not expected to improve or worsen) but have not returned to baseline.
Not recovered/Not Resolved	The effects of the event are still present and changing. The event is not considered stabilized or resolved.
Recovered/Resolved with Sequelae	The subject has fully recovered from the event with some observable residual effects.
Fatal	The event was the primary cause of death (may or may not be the immediate cause of death).
Unknown	The event outcome is unknown.

Death is an outcome of an event and not an event per se. Sudden death or death due to unexplainable cause(s) is to be reported, but follow-up will be pursued until cause of death is determined.

Action Taken with Study Drug

Action taken with study drug in relation to each adverse event will be characterized as follows:

None

Drug withdrawn

Drug interrupted

Unknown

Not applicable

Other (specify on CRF)

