9.2 Adverse Events

9.2.1 **Definitions of Adverse Events**

According to the Code of Federal Regulations, 21 CFR Parts 312.32 and 320.32 (IND Safety Reporting, Applicability of requirements regarding an "Investigational New Drug Application"), FDA Guidance for Industry (Investigational New Drug Safety Reporting Requirements for Human Drug and Biological Products and Safety Reporting Requirements for Bioavailability and Bioequivalence Studies in Humans) (Federal Register/Vol. 75, No. 188/September 29, 2010) and ICH E2A (Clinical Safety and Data Management: Definitions and Standards for Expedited Reporting):

CONFIDENTIAL

An adverse event (AE) means any untoward medical occurrence associated with the use of a drug in humans, whether or not considered drug related.

A suspected adverse reaction means any AE for which there is a reasonable possibility that the drug caused the AE.

The following information should be considered when determining whether or not to classify a test result, medical condition, or other incident as an adverse event:

Adverse events will be recorded from the time of informed consent.

Abnormal laboratory values should not generally be recorded as an adverse event unless an intervention is required, the laboratory abnormality results in a serious adverse event, the lab abnormality results in study termination or interruption/discontinuation of study treatment, or the lab abnormality is associated with clinical signs or symptoms. When recording an adverse event resulting from a laboratory abnormality, the resulting medical condition rather than the abnormality itself should be recorded (e.g., record "anemia" rather than "low hemoglobin").

Complications that occur in association with a protocol-mandated intervention (e.g., invasive procedures such as biopsies) should be recorded as AEs.

Whenever possible, the Investigator should group signs or symptoms that constitute a single diagnosis under a single event term. For example, cough, rhinitis, and sneezing might be grouped together as "upper respiratory tract infection". If possible, abnormal laboratory results that meet the definition of an adverse event (see above) should be reported as a clinical diagnosis rather than the abnormal value itself (e.g., "anemia" rather than "decreased blood count").

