9.2.1.1 Documentation and Monitoring Adverse Events

All AEs encountered during the clinical trial following subject consent through the last dose of study drug will be recorded on the appropriate Adverse Events case report form (eCRF).

Special considerations:

Elective procedures or routinely scheduled treatments are not considered AEs. However, an untoward medical event occurring in association with a prescheduled elective procedure should be recorded as an AE.

A baseline condition is not considered an AE unless the condition worsens following study drug administration.

Death itself is not considered an AE; it is, instead, the outcome of an AE.

SAEs that are considered related (i.e., determined to be possibly, probably, or definitely related) to sofpironium bromide by the Investigator or Sponsor should be followed until the event resolves or stabilizes (see Section 9.3.1).

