9.4 Adverse Events

Treatment-emergent adverse events (TEAEs) are defined as those adverse events (AEs) with onset after the first dose of study drug or existing events that worsened after the first dose during the study. Treatment-emergent AEs will be summarized by treatment group. Partial or missing start or end dates will be imputed per Section 9.1.1.

Verbatim terms on case report forms will be mapped to preferred terms and system organ classes using the latest version of MedDRA.

At Weeks 2, 4, 6, 12, 24, 48 and 52, treatment-emergent adverse events (TEAEs, i.e., AEs occurring during or after treatment initiation) will be summarized in the following tables: all reported TEAEs, all treatment-related TEAEs, severe TEAEs, TEAEs leading to dose interruption, TEAEs leading to dose modification, TEAEs leading to study discontinuation, TEAEs of special interest, and anticholinergic TEAEs. Two sets of the above tables will be produced: (a) for cumulative TEAEs up to the current visit reported by those making the visit, and (b) for cumulative TEAEs up to the current visit reported by all Safety Population subjects (including those absent from the current visit). At each of the 7 indicated weeks, each of the above tables will summarize the subject incidence (frequency count and %) for the specified TEAE, mapped to MedDRA System Organ Class and Preferred Term, according to the highest severity reported. Subjects with only unknown severity for a TEAE will be counted under the severity unknown category. Additionally, serious TEAEs and treatment-related serious TEAEs will be summarized in the same manner for all data through Week 52.

Version: 1.0 Page 26 of 51

Summaries that are displayed by system organ class and preferred terms will be ordered by descending incidence of system organ class in the combined BBI-4000 group and preferred term within each system organ class. The combined BBI-4000 group will not be displayed and will only be used for sorting. TEAEs of special interest include the following:

- Vision blurred
- Mydriasis
- Urinary hesitation
- Pupils unequal

Adverse event data will be presented in data listings by subject, treatment group, and event. Serious TEAEs and TEAEs leading to discontinuation of the study will be presented in separate data listings. Death is not expected. However, should death occur on study, the event will be reported with detailed narratives.

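### The causality scale makes a known or expected response pattern a condition of every related category, so a truly novel reaction has no related rating under the protocol's own table

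*Protocol*

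**What the plan says.** Protocol 9.2.1.2 gives one five-level table for relating an AE to study drug and calls it guidelines. All three related levels need reasonable timing and a recognised pattern:

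- Definitely Related: an event "that follows a known or expected response pattern to the test article; and that is confirmed by improvement on stopping or reducing the dosage", and also confirmed on rechallenge.
- Probably Related: the same pattern and dechallenge conditions, with other causes unlikely.
- Possibly Related: an event "that follows a known or expected response pattern to the test article; but may have been caused by concurrent/underlying illness", or by another drug, procedure or cause.

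Unlikely Related covers an event lacking reasonable timing, or one "that does not follow a known or expected response pattern to the test article, or most likely was caused by concurrent/underlying illness", and so on. Not related means almost certainly due to something else.

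Protocol 9.2.1 sets a different test: "A suspected adverse reaction means any AE for which there is a reasonable possibility that the drug caused the AE". It has no expectedness condition.

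Protocol 9.2.1.1 shows which ratings count as related, but only for follow-up: it concerns "SAEs that are considered related (i.e., determined to be possibly, probably, or definitely related) to sofpironium bromide by the Investigator or Sponsor". SAP 9.4 plans tables at seven visits for "all reported TEAEs, all treatment-related TEAEs, severe TEAEs" and five further groups, plus a treatment-related serious TEAE table through Week 52. It does not say which ratings make a TEAE treatment-related.

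**The concern.** Whether an event was caused by the drug and whether it was expected are separate questions, and the table merges them. This matters more here than in many trials. The primary objective is long-term safety. Where the prior-experience summaries in Protocol Section 1 state a repeat-dosing duration, it is 14 to 42 days, against 48 weeks here. An effect that appears only with longer use may have no established pattern.

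The trial is also open-label with two active arms and no vehicle. No hypothesis tests are planned (SAP 3.1) and there is no data monitoring committee (SAP 12). Apart from a descriptive comparison of the two concentrations, the relatedness rating is the main planned way to separate drug effects from background events. If the rating excludes novel effects by definition, the treatment-related tables can mainly confirm what is already known.

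Some conduct also depends on the rating. Follow-up of an SAE until it resolves or stabilises applies to related SAEs (Protocol 9.2.1.1, 9.3.1, 9.4). Reporting of an SAE after study completion applies if the Investigator considers it related (Protocol 9.3.1).

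**Working it through.** The plan states no figure to reproduce. The check is one of logic, followed by a count of tables.

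**Step 1: reduce each row to its conditions.** T = reasonable timing, K = known or expected pattern, D = improvement on stopping or reducing, R = recurrence on rechallenge, O = another cause.

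| Category | Condition |
|---|---|
| Definitely | T and K and D and R |
| Probably | T and K and D, with O unlikely |
| Possibly | T and K, with O possible |
| Unlikely, clauses as alternatives | not T, or not K, or O most likely |
| Unlikely, semicolon read as in the related rows | (not T and not K), or O most likely |
| Not related | O almost certain |

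**Step 2: test a novel reaction.** Set T = yes, K = no, D = yes, O = no.

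- Definitely, Probably and Possibly all fail on K, so 3 of 3 related categories are closed.
- With the Unlikely clauses as alternatives, the event is Unlikely Related.
- With the semicolon read as it must be in the related rows, the event is neither Unlikely nor Not related. It has no category.

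**Step 3: isolate the cause.** Change only K to yes and the same event meets Probably Related. The pattern condition alone closes the related categories.

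**Step 4: compare with 9.2.1.** Plausible timing, improvement on stopping and no other cause would ordinarily amount to a reasonable possibility of causation. The event is then a suspected adverse reaction under 9.2.1 but cannot be rated related under 9.2.1.2.

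**Step 5: count the affected outputs.** SAP 9.4 lists 8 visit-based TEAE groups: all, treatment-related, severe, dose interruption, dose modification, study discontinuation, special interest and anticholinergic. Each is produced at 7 weeks (2, 4, 6, 12, 24, 48, 52) for 2 denominators.

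- All visit-based tables: 8 × 7 × 2 = 112.
- Treatment-related: 1 × 7 × 2 = 14 (Tables 14.3.1.4.3 and .4 through 14.3.1.10.3 and .4), and 14/112 = 12.5%.
- Not based on relatedness: 112 − 14 = 98.
- In addition, one treatment-related serious TEAE table (14.3.1.3).

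**The case against.** A reader might infer that every new reaction is forced into Unlikely Related and lost from the safety results. The documents do not support that, for five reasons.

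- **The pattern may be known or expected.** The risk discussion in Protocol Section 1 lists anticholinergic class effects such as urinary retention and tachycardia, and leaves the list open. A first occurrence in the programme that fits this pharmacology meets the condition. Only events outside it are affected.
- **The Unlikely row is ambiguous.** As Step 2 shows, one reading leaves the event unclassified rather than Unlikely.
- **Capture does not depend on relatedness.** The event appears by system organ class and preferred term in the all-TEAE tables, and where applicable in the severe, interruption, modification or discontinuation tables.
- **In-study SAE reporting is protected.** Every SAE goes to the Sponsor within 24 hours whatever the suspected causality (Protocol 9.3.1). For follow-up, the Sponsor may also judge an SAE related (9.2.1.1, 9.4).
- **The table is called guidelines.** An Investigator may depart from it. A literal reading rates no such event as related, but that is a logical result and not an estimate of what sites do.

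These points stand and limit the consequence, but they do not remove the inconsistency. No other causality rule is given, and uneven departures across about 30 sites would make the ratings inconsistent. No Sponsor causality review is described for non-serious TEAEs, and post-study SAE reporting rests on the Investigator's judgement alone.

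Two links remain uncertain. The mapping from ratings to treatment-related is borrowed from the SAE follow-up text. The protocol supplied is Amendment 01, while the SAP is based on Amendment 4 dated 6 May 2019, so the table may have changed.

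**Conclusion.** The inconsistency between 9.2.1 and 9.2.1.2 is real on the text supplied. A reaction outside known or expected pharmacology, with plausible timing and no other cause, has no related category.

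The reach is limited: the 14 treatment-related TEAE tables and, for a serious event, the treatment-related SAE table. Follow-up of such an SAE to resolution would depend on the Sponsor's own judgement, and a post-study SAE report could be missed. The other 98 visit-based tables do not depend on relatedness, and in-study SAE reporting is unaffected.

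The effect on the tables rests on three assumptions: sites apply the table as written, treatment-related means possibly, probably or definitely related, and the table is unchanged in Amendment 4. How many events would be affected cannot be estimated from the documents. This should be fixed, because the tables concerned serve the primary objective and the remedy is small. A higher rating is not justified, because capture does not depend on causality.

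**What to change.** First confirm how the relationship table reads in Amendment 4. If it is unchanged:

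1. In Protocol 9.2.1.2, remove the pattern condition from Definitely, Probably and Possibly Related (at minimum from Possibly Related), and remove its negation from Unlikely Related. Leaving it in Definitely Related alone would still bar a novel effect confirmed by rechallenge from that rating.
2. Base Possibly Related on a reasonable possibility of causation, in line with 9.2.1. Have the Sponsor assess expectedness separately.
3. State in SAP 9.4 that treatment-related means rated possibly, probably or definitely related.
4. For data already recorded, keep the Investigator ratings as primary. Any medical review of Unlikely-rated TEAEs should use pre-specified criteria, be masked to dose arm where possible, and be shown only as a supplementary listing or table. Replacing ratings before lock in an open-label trial would mix two rating rules and could bias the comparison of 5% with 15%.

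The cost is a wording change to one table, a memo to sites, one SAP sentence and, if wanted, a bounded review. Treatment-related counts may rise slightly, and ratings made before and after the change will not be fully comparable. The study report should say so.

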9.3 Serious Adverse Events

Any AE that is serious (see definition below) and occurs after administration of study drug must be reported to the Sponsor within 24 hours of discovery of the event. An event occurring after informed consent but before administration of study drug that is considered serious and possibly related to a protocol procedure must also be reported to the Sponsor within 24 hours of discovery of the event.

9.3.1 **Definition and Reporting Procedures**

An AE should be classified as an SAE if it meets one of the following criteria:

Fatal:	The adverse event resulted in death.
Life Threatening:	The adverse event placed the patient at immediate risk of death. This classification does not apply to an adverse event that hypothetically might cause death if it were more severe.
Hospitalization:	The AE required or prolonged an existing inpatient hospitalization. Hospitalizations for elective medical or surgical procedures or treatments planned before the signing of informed consent in the study or routine check- ups are not serious adverse events by this criterion. Hospitalizations or prolonged hospitalizations for scheduled therapy need not be captured as SAEs.
Disabling/Incapacitating:	Resulted in a substantial and permanent disruption of the patient's ability to carry out activities of daily living.
Congenital Anomaly or Birth Defect:	An adverse outcome in a child or fetus of a patient exposed to the study drug or study treatment regimen before conception or during pregnancy.
Medically Significant:	The adverse event did not meet any of the above criteria, but could have jeopardized the patient and might have required medical or surgical intervention to prevent one of the outcomes listed above.

Every SAE (regardless of suspected causality) should be reported to the Sponsor within 24 hours of discovery of the event. The processes for reporting and documenting SAEs are provided in the study manual. Investigators are responsible for reporting these events to their Institutional Review Board/Institutional Ethics Committee (IRB/IEC) in accordance with federal and institutional laws and regulations.

Additional updates from the Investigator may be necessary as more information becomes available on the SAE, and all treatment-related SAEs will be followed until the acute event has resolved or stabilized, even if the subject discontinues study participation prior to the SAE resolution. Any new information or follow-up information pertaining to previously reported SAEs will be reported to the Sponsor within 24 hours of becoming aware of the new or follow-up information. The new or follow-up information should be faxed to the Sponsor at [name] or emailed to [contact].

Any SAE that occurs after study completion, and is considered by the Investigator to be related to sofpironium bromide, should be reported to the Sponsor.

Reporting Serious Adverse Events to Regulatory Agencies

The Sponsor will determine which SAEs qualify for expedited reporting to regulatory agencies. SAEs that qualify for expedited reporting will be submitted to regulatory agencies in accordance with federal regulation (21CFR 312.32).

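### The SAE disability criterion requires permanence, so some prolonged but reversible incapacity is not classed as serious, no upgrade rule covers it, and serious TEAE counts may be understated

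*Protocol*

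**What the plan says.** Protocol 9.3.1 lists six criteria and needs only one: "An AE should be classified as an SAE if it meets one of the following criteria". Four of them matter here.

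- Disabling/Incapacitating: "Resulted in a substantial and permanent disruption of the patient's ability to carry out activities of daily living".
- Hospitalization: "The AE required or prolonged an existing inpatient hospitalization".
- Life Threatening: the subject was at immediate risk of death.
- Medically Significant: an event meeting none of the other criteria that "could have jeopardized the patient and might have required medical or surgical intervention to prevent one of the outcomes listed above".

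The same section sets the clock: "Every SAE (regardless of suspected causality) should be reported to the Sponsor within 24 hours of discovery of the event". The rule for later information is limited to events already reported as serious: "Any new information or follow-up information pertaining to previously reported SAEs will be reported to the Sponsor within 24 hours".

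Protocol 9.2.1.2 defines grade 3 (Severe) as "Incapacitating with inability to work or do usual activity", with no condition on duration or permanence. It adds that "a severe adverse event is not necessarily serious".

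SAP 9.4 summarizes serious TEAEs and treatment-related serious TEAEs once, for all data through Week 52 (Tables 14.3.1.2 and 14.3.1.3). SAP 13 explains that SAEs are expected to be few. SAP 9.4 also tabulates all TEAEs and severe TEAEs cumulatively at seven weeks, in two sets.

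**The concern.** Safety is the primary objective (Protocol 3.1; SAP 2.1), and SAP 12 plans no data monitoring committee. The serious label therefore carries weight. It starts the 24-hour notification to the sponsor, and it is the pool from which the sponsor selects events for expedited reporting to regulatory agencies.

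The permanence condition fits poorly with what the protocol expects of the drug. Protocol 1 describes anticholinergic effects in earlier studies as mostly mild or moderate and short-lived, and says TEAEs resolved once treatment stopped. If harms are expected to reverse, a disability criterion that requires permanence will seldom be met by the effects under watch, even in the uncommon case where one of them incapacitates a subject for some time.

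The condition also depends on something a site usually cannot know on the day it learns of the event. The protocol does not tell the site how to classify an event whose permanence is only suspected, or what to do when a non-serious event later proves to meet a criterion.

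**Working it through.** The plan states no SAE rate, power or event count that depends on this definition, so there is no figure to reproduce. The check is a reading of the criteria, followed by an illustration under assumed rates.

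**Step 1: run one case through the six criteria.** Take a subject who cannot carry out usual activity for a prolonged period and then recovers, without admission, without immediate risk of death, and with no intervention needed to avert a listed outcome.

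| Criterion (Protocol 9.3.1) | Met? | Reason |
|---|---|---|
| Fatal | No | Subject recovers |
| Life Threatening | No | No immediate risk of death |
| Hospitalization | No | Not admitted |
| Disabling/Incapacitating | No | Substantial, but not permanent |
| Congenital anomaly | No | Not applicable |
| Medically Significant | No | Needs both jeopardy and a possible intervention to avert a listed outcome |

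The event is Severe by Protocol 9.2.1.2 and non-serious by 9.3.1.

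**Step 2: how far does Medically Significant close the gap?** In part. The listed outcomes include hospitalization, so an incapacitating event that might have needed treatment to avoid admission can qualify. On the disability side, the outcome to be averted is itself the permanent one, so the condition carries over. What remains outside is reversible incapacity with no admission, no immediate risk of death and no such intervention.

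**Step 3: what happens over time?** Notification runs from discovery, when permanence is usually unknown. The 24-hour update rule covers only SAEs already reported. Follow-up until resolution or stabilization is required for SAEs considered related (Protocol 9.2.1.1, 9.3.1, 9.4). AE collection ends at the latest at the final study visit (Protocol 9.4), and an SAE occurring after study completion is reported only if considered related. An event not yet called serious thus has no stated path by which permanence would be established after that visit.

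**Step 4: possible size.** Let p be the per-subject probability of an event that incapacitates, reverses and meets no other criterion. The documents give no value, so p is an assumption. With n subjects, the expected number is n × p and the chance of at least one is 1 − (1 − p)^n. Planned arm sizes are 100 (5% gel) and 200 (15% gel), total 300 (Protocol 2).

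| Assumed p | Expected in 100 / 200 / 300 | Chance of at least one in 300 |
|---|---|---|
| 0.1% | 0.1 / 0.2 / 0.3 | 1 − 0.999^300 = 26% |
| 0.25% | 0.25 / 0.5 / 0.75 | 1 − 0.9975^300 = 53% |
| 0.5% | 0.5 / 1.0 / 1.5 | 1 − 0.995^300 = 78% |
| 1% | 1 / 2 / 3 | 1 − 0.99^300 = 95% |

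Each unclassified subject lowers the serious TEAE percentage by 100 × 1/100 = 1.0 point in the 5% arm, or 100 × 1/200 = 0.5 point in the 15% arm. If p is zero, nothing changes.

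**The case against.** A fair defence makes five points.

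1. *An undercount is not shown.* This stands. A reader might infer that serious TEAE counts will read low. The documents give no rate for such events, they describe anticholinergic effects as predominantly mild or moderate, and the loss may be nil. The SAP's expectation of few SAEs only explains why it plans one table instead of several.

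2. *A reporting clock affects timing, not the final count.* This also stands. Seriousness is recorded for each AE on the eCRF, and nothing bars a later change of classification. A reader might infer that the 24-hour limit itself removes events from the tables. It does not. An event is lost from the count only if it is not permanent or if its permanence is never established. What remains is the missing upgrade rule.

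3. *The events stay visible.* True for the outputs: they remain in the all-TEAE tables and the AE listing and, if graded Severe, in the severe-TEAE tables. Depending on the event, they may also appear in the interruption, modification, discontinuation, anticholinergic or special-interest tables. That does not restore prompt notification or the serious label.

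4. *Severe and serious are different scales.* Correct, and the protocol says so. The shared word for incapacity is an overlap in labelling, not a contradiction.

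5. *The standard cannot be checked here.* Correct. Protocol 9.2.1 cites 21 CFR 312.32 and ICH E2A but does not reproduce their disability wording, so a departure from them cannot be confirmed from these documents. The study manual on SAE procedures is not available either. The protocol text reviewed is Amendment 01, while SAP 1 follows Amendment 4, so the criterion may have changed.

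**Conclusion.** The point holds in a limited form. As written, 9.3.1 withholds the serious label and 24-hour notification from prolonged, reversible incapacity that is not life-threatening, needs no admission and needs no intervention to avert a listed outcome. This follows from a stated condition, not from missing detail. The lack of a rule for suspected permanence or later upgrade adds to it.

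Serious TEAE counts may be understated as a result, but the documents do not establish that they will be. The size is unknown and may be zero; the rates in the working are assumptions. No hypothesis test, sample size calculation or stopping rule in the plan depends on the SAE count. The practical stake is safety escalation and the completeness of two summary tables. The conclusion assumes that the Amendment 01 wording still applies and that the study manual does not already fill the gap.

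**What to change.** 1. Check the disability criterion in the current amendment and against the regulation cited in Protocol 9.2.1. If the permanence condition is still there, remove it.
2. State in 9.3.1 that an AE first recorded as non-serious is upgraded, and reported to the sponsor within 24 hours, when the site learns that it meets a seriousness criterion.
3. Before database lock, re-review AEs graded Severe but recorded as non-serious against the revised criterion, and correct the classification where needed so that Tables 14.3.1.2 and 14.3.1.3 reflect it.

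The cost is one changed definition line and a short upgrade statement, with the sponsor and IRB approval that Protocol 12.3 requires for an amendment, plus a small listing review. The SAE count may rise slightly. No dose, schedule or treatment rule changes.
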